### APPENDIX B: CLINICAL LABORATORY ANALYTES

# **Standard Safety Chemistry Panel**

Alanine aminotransferase Albumin
Alkaline phosphatase Amylase
Aspartate aminotransferase Bicarbonate
Blood urea nitrogen Calcium

Chloride Creatine kinase

Creatinine Estimated glomerular filtration rate [1]

Gamma-glutamyl transferase Glucose (fasting)
High-sensitivity C-reactive protein Inorganic phosphorus

Lactate dehydrogenase Lipase
Potassium Sodium
Total bilirubin Total protein

Uric acid

[1] Calculated using the Chronic Kidney Disease Epidemiology Collaboration equation: https://www.mdcalc.com/ckd-epi-equations-glomerular-filtration-rate-gfr.

## **Endocrinology**

Follicle-stimulating hormone [1]

[1] Follicle-stimulating hormone test will be performed in peri-menopausal women, defined as women <55 years of age for whom it has been  $\ge 1$  year since their last menstrual period.

## Hematology

Glycosylated hemoglobin (HbA1c) [1] Hematocrit Hemoglobin Platelets

Red blood cell count and differential [2]

[1] Screening Visit only.

[2] Manual microscopic review is performed only if white blood cell count and/or differential values are out of reference range.

# Urinalysis

Bilirubin Blood Glucose Ketones

Leukocyte esterase Microscopy [1]

Nitrite pH

Protein Specific gravity

Urobilinogen

[1] Microscopy is performed only as needed based on positive dipstick test results.

# **Pregnancy Test**

Urine

# **Lipid Profile**

Apolipoprotein B Apolipoprotein E (ApoE)

High-density lipoprotein-ApoE [1] High-density lipoprotein cholesterol
Low-density lipoprotein cholesterol [2] Non-high-density lipoprotein cholesterol
Triglycerides Very low-density lipoprotein cholesterol

[1] With and without apolipoprotein C3.

[2] At all visits, LDL-C will be calculated using the Friedewald formula. In addition, at Visit 2 and Visit 4, LDL-C will also be measured by preparative ultracentrifugation, also referred to as beta quantification.

# **APPENDIX C: DIET GUIDELINES**

The table below describes guidelines for the Therapeutic Lifestyle Changes diet:

Component	Recommendation
Saturated fats	<7% of total calories
Total fat	25% to 35% of total calories
Dietary cholesterol	<200 mg/day
Sodium	<2400 mg/day
	Adjust total caloric intake to maintain desirable body weight and/or prevent
Total calories	weight gain

Adapted from the United States National Institutes of Health Therapeutic Lifestyle Changes [TLC] diet.

Appendix A: References .		
Appendix B: Clinical Labo	ratory Analytes	23

LIST OF ABBREVIATIONS

Abbreviation	Definition
ADaM	Analysis Data Model
AE	Adverse event
ANCOVA	Analysis of Covariance
АроВ	Apolipoprotein B
ApoC3	Apolipoprotein C3
АроЕ	Apolipoprotein E
ATC	Anatomical therapeutic chemical
CDISC	Clinical Data Interchange Standards Consortium
CETP	Cholesteryl ester transfer protein
CRF	Case report form
CSR	Clinical Study Report
ECG	Electrocardiogram
FSH	Follicle-stimulating hormone
HbA1c	Glycosylated hemoglobin
HDL	High-density lipoprotein
HDL-C	High-density lipoprotein cholesterol
ICF	Informed consent form
IRT	Interactive response technology
ITT	Intent-to-Treat
LDL-C	Low-density lipoprotein cholesterol
LOCB	Last Observation Carried Backward
MedDRA	Medical Dictionary for Regulatory Activities
mITT	Modified Intent-to-Treat
MMRM	Mixed model for repeated measures
Non-HDL-C	Non-high-density lipoprotein cholesterol
РК	Pharmacokinetics
PP	Per-Protocol
PUC	Preparative ultracentrifugation
SAE	Serious adverse event
SAP	Statistical Analysis Plan
SDTM	Study Data Tabulation Model
TEAE	Treatment-emergent adverse event
TESAE	Treatment-emergent serious adverse event
TFL	Tables, figures, and listings
TG	Triglycerides
TLC	Therapeutic Lifestyle Changes
VLDL-C	Very low-density lipoprotein cholesterol
WHO	World Health Organization

1 INTRODUCTION

The purpose of this Statistical Analysis Plan (SAP) is to provide a description of the statistical methods to be implemented for the analysis of data from NewAmsterdam Pharma BV Protocol TA-8995-303. The SAP will be finalized prior to database lock. Any deviations from the SAP after database lock will be documented in the final Clinical Study Report (CSR).

2 STUDY OVERVIEW

2.1 Study Objectives

2.1.1 Primary Objective

The primary objective of this study is as follows:

• To evaluate the effect of obicetrapib in combination with ezetimibe compared to placebo on low-density lipoprotein cholesterol (LDL-C) at Day 57.

2.1.2 Secondary Objectives

The secondary objectives of this study include the following:

- To evaluate the effect of obicetrapib monotherapy compared to placebo on LDL-C at Day 57;
- To evaluate the effect of obicetrapib in combination with ezetimibe compared to placebo on apolipoprotein B (ApoB) at Day 57;
- To evaluate the effect of obicetrapib monotherapy compared to placebo on ApoB at Day 57;
- To evaluate the effect of obicetrapib in combination with ezetimibe compared to ezetimibe monotherapy on LDL-C at Day 57;
- To evaluate the effect of obicetrapib monotherapy compared to ezetimibe monotherapy on LDL-C at Day 57;
- To evaluate the effect of ezetimibe monotherapy compared to placebo on LDL-C at Day 57; and
- To evaluate the effect of obicetrapib in combination with ezetimibe compared to ezetimibe monotherapy on ApoB at Day 57.

2.1.3 Exploratory Objectives

The exploratory objectives of this study include the following:

- To evaluate the effect of ezetimibe monotherapy compared to placebo on ApoB at Day 57;
- To evaluate the effect of obicetrapib alone, ezetimibe alone, and obicetrapib in combination with ezetimibe on non-high-density lipoprotein cholesterol (non-HDL-C), very low-density lipoprotein cholesterol (VLDL-C), high-density lipoprotein cholesterol (HDL-C), triglycerides (TG), apolipoprotein E (ApoE), and high-density lipoprotein (HDL)-ApoE (with and without apolipoprotein C3 [ApoC3]) at Day 57;
- To evaluate the effect of obicetrapib alone, ezetimibe alone, and obicetrapib in combination with ezetimibe on the proportion of participants achieving predefined LDL-C targets at Day 57;

- To assess the mean trough plasma levels of obicetrapib alone, ezetimibe alone, and obicetrapib in combination with ezetimibe at steady state on Day 57, Week 12, and Week 16;
- To evaluate the effect of obicetrapib alone, ezetimibe alone, and obicetrapib in combination with ezetimibe on cholesteryl ester transfer protein (CETP) mass at Day 57, Week 12, and Week 16; and
- To evaluate the safety and tolerability profiles of obicetrapib alone, ezetimibe alone, and obicetrapib in combination with ezetimibe assessed by clinical laboratory values and incidence of adverse events (AEs).

2.2 Study Design

2.2.1 Overview

This study will be a placebo-controlled, double-blind, randomized Phase 2 study in participants with mild dyslipidemia to evaluate the efficacy, safety, and tolerability of obicetrapib and ezetimibe combination therapy. The study will take place at approximately 10 to 15 sites in North America and Europe as appropriate.

This study consists of a Screening Visit (Visit 1), a Treatment Period (8 weeks, Visits 2 to 4), a Safety Follow-up Visit (Visit 5), and a Pharmacokinetic Visit (Visit 6). The expected study duration for participants entering on the study since Screening Visit is approximately 20-weeks. Please refer to Table 1. Schedule of Procedures) below for details.

At the Screening Visit (Visit 1), participants will be required to sign an informed consent form (ICF) before any study-related procedures are performed. After signing the ICF, participants will be assessed for study eligibility. Participants will also receive counselling regarding the Therapeutic Lifestyle Changes diet and will receive instructions on how to follow this diet. Participants will be required to begin the diet starting at the Screening Visit.

Up to 2 weeks after the Screening Visit, participants will return to the site on Day 1 (Visit 2) to be randomized and begin treatment. Approximately 100 eligible participants (25 participants per treatment group) will be randomized in a 1:1:1:1 ratio to 1 of the following treatment groups:

- Combination therapy: 5 mg obicetrapib + 10 mg ezetimibe;
- Obicetrapib monotherapy: 5 mg obicetrapib + placebo ezetimibe;
- Ezetimibe monotherapy: placebo obicetrapib + 10 mg ezetimibe; or
- Placebo: placebo obicetrapib + placebo ezetimibe.

During the 8-week Treatment Period, the assigned study drugs will be administered by the participant orally and once daily on Days 1 through 57. Participants will return to the site every 4 weeks for efficacy, safety, pharmacokinetics (PK), and CETP mass assessments.

Participants will return to the site for a Safety Follow-up Visit (Visit 5) approximately 4 weeks after the end of the Treatment Period for safety, PK, and CETP mass assessments.

Participants will return to the site for a PK Visit (Visit 6) approximately 8 weeks after the end of the Treatment Period for PK and CETP mass assessments.

CONFIDENTIAL

Table 1. Schedule of Procedures

	0	Т	reatm		Safety	DIC	
N 12 - 14	Screening		Perio		Follow-up	PK	Early
Visit	1	2	3	4	5	6	Termination
Week	Up to -2	0	4	8	12	16	Visit
			29	57		113	
Day (±Visit Window)	-14 to -1	1	(±3)	(±3)	85 (±3)	(±7)	Unscheduled
Informed consent ^a	X						
Inclusion/exclusion							
criteria	X	X⁵					
Demographic							
information	X	I					
Medical/surgical history	Х						
Prior/concomitant							
medications	X	X	X	X	Х		 
Weight and height ^c	Х			Х			X
Physical examination	Х			Х			Х
Vital signs ^d	Х	X	X	Х	Х		Х
12-lead ECG ^e	Х						
Urine pregnancy test ^r	X			· ·····			
FSH test ⁹	X						
Fasting (≥10 hours)							
chemistry and							
hematology ^h	X X	X	Х	X	X X		X X
Urinalysis	X	Х	Х	Х	Х		X
Fasting (≥10 hours) lipid							
profile ⁱ	X	X	Х	Х			X
PK sample ⁱ		Х		X	Х	Х	
CETP mass sample ⁱ		Х		X	Х	Х	
Randomization		Х					
Dispense study drugs,							
as appropriate		Х	X				
Study drug							
administration ^k		Х	X	X			
Study drug compliance							
check			Х	X			X
TLC diet counseling	X	Х	Х				
Register visit in IRT	X	Х	Х	Х			Х
Adverse event			1			Х	
assessment		X	X	X	X		X

Note:

a. Signed informed consent must be obtained before any study-related procedures are performed.

b. Any updates since the Screening Visit will be assessed.

c. Height and weight will be measured at the Screening Visit and will be used to calculate body mass index. Weight only will be measured at all other visits as indicated. Measurement of weight should be performed with the participant dressed in indoor clothing, with shoes removed, and bladder empty.

d. Vital signs will include body temperature, heart rate, and triplicate blood pressure (systolic and diastolic) measurements.

e. A single, standard 12-lead ECG will be performed by the Investigator or trained site personnel at the Screening Visit and centrally read by

f. For women of childbearing potential only.

g. FSH test will be performed in peri-menopausal women, defined as women <55 years of age for whom it has been >1 year since

their last menstrual period.

h. At Screening Visit only, hematology panel will include HbA1c.

i. At all visits, LDL-C will be calculated using the Friedewald formula. In addition, at Visit 2 and Visit 4, LDL-C will also be measured by preparative ultracentrifugation, also referred to as beta quantification.

k. Study drugs will be administered by the participant orally and once daily on Days 1 through 57. Study drugs should be administered at approximately the same time each morning, with food. On days with visits scheduled, study drugs should be administered with food following all fasted blood samples.

1. Participants will be instructed to begin the TLC diet at the Screening Visit.

CETP = cholesteryl ester transfer protein; ECG = electrocardiogram; FSH = follicle-stimulating hormone; HbAlc = glycosylated hemoglobin; IRT = interactive response technology; PK = pharmacokinetic; TLC = Therapeutic Lifestyle Changes.

2.2.2 Randamization and Blinding

Participants who meet all eligibility criteria will be randomized into the study. Participants will be randomized in a 1:1:1:1 ratio to the combination therapy, obicetrapib monotherapy, ezetimibe monotherapy, or placebo treatment groups. At randomization, participants will be stratified according to their Screening Visit (Visit 1) LDL-C value (<3.5 mmol/L [<135 mg/dL] or \geq 3.5 mmol/L [\geq 135 mg/dL]). An automated interactive response technology (IRT) system will be used to assign the participant to 1 of the 4 treatment groups.

Participants, Investigators, the Clinical Research Organization, and the Sponsor will be blinded to all lipid results from Day 1 (Visit 2) for the first participant through the PK Visit (Visit 6) for the last participant in order to protect blinding to treatment assignment.

2.2.3 Study Drug

The study drugs used in this study are as follows:

- 5 mg obicetrapib tablet;
- 10 mg ezetimibe tablet, over-encapsulated into a capsule;
- Placebo tablet for obicetrapib; and
- Placebo capsule for ezetimibe.

Participants will be randomized to receive 2 of the study drugs listed above for the duration of the study.

At each appropriate visit (Visits 2 and 3), participants will receive a kit containing blister cards with the 2 study drugs appropriate for the participant's treatment group. Participants will be instructed to take 2 units (1 tablet + 1 capsule) from the blister cards in the kit each day. The blister cards will be clearly labelled to indicate which blisters to use on each day. Each kit will provide a sufficient supply for 1 month of dosing. Participants will be instructed to return all unused study drugs at the next visit.

Compliance to the study drug regimen will be evaluated by counting unused tablets and capsules. During the Treatment Period, if compliance is not between 80% and 120%, inclusive, the participant will be counselled about the importance of compliance to the regimen and protocol deviation documented. If the limits are exceeded at 2 consecutive visits, a decision will be made by the Investigator and Sponsor as to whether the participant should be withdrawn from the study.

j. Samples will be stored for future analysis.

2.2.4 Sample Size Determination

A sample size of at least 100 evaluable participants (ie, 25 participants per treatment group) will provide >90% power to detect a 30% difference in LDL-C reduction at Day 57 (SD 15%) for the combination therapy group compared to the placebo group at a 2-sided significance level of 0.05.

The sample size for this study was determined in order to provide sufficient power (>80%) for the analyses of the primary efficacy endpoint and secondary efficacy endpoints described in Section 2.3. The sample size calculations used values reported from a previous clinical trial involving obicetrapib (TA-8995) as a starting point for the assumptions of the treatment difference and standard deviation¹. This sample size will also contribute sufficient participant exposure and safety data.

2.3 Study Endpoints

2.3.1 Primary Efficacy Endpoint

The primary efficacy endpoint is percent change from Day 1 to Day 57 in LDL-C, for the combination therapy group compared to the placebo group.

2.3.2 Secondary Efficacy Endpoints

The secondary efficacy endpoints include the following, in hierarchical order:

- Percent change from Day 1 to Day 57 in LDL-C for the obicetrapib monotherapy group compared to the placebo group;
- Percent change from Day 1 to Day 57 in ApoB for the combination therapy group compared to the placebo group;
- Percent change from Day 1 to Day 57 in ApoB for the obicetrapib monotherapy group compared to the placebo group;
- Percent change from Day 1 to Day 57 in LDL-C for combination therapy group compared to the ezetimibe monotherapy group;
- Percent change from Day 1 to Day 57 in LDL-C for the obicetrapib monotherapy group compared to the ezetimibe monotherapy group;
- Percent change from Day 1 to Day 57 in LDL-C, for the ezetimibe monotherapy group compared to the placebo group; and
- Percent change from Day 1 to Day 57 in ApoB for the combination therapy group compared to the ezetimibe monotherapy group.

2.3.3 Exploratory Efficacy Endpoints

The exploratory efficacy endpoints include the following:

- Percent change from Day 1 to Day 57 in ApoB for the ezetimibe monotherapy group compared to the placebo group;
- Pairwise comparisons among the various treatment groups for the percent change from Day 1 to Day 57 in non-HDL-C, VLDL-C, HDL-C, TG, ApoE, and HDL-ApoE (with and without ApoC3);
- Pairwise comparisons among the various treatment groups for the proportion of participants at Day 57 that achieve LDL-C <2.6 mmol/L (<100 mg/dL), LDL-C <1.8 mmol/L (<70 mg/dL), and LDL-C <1.3 mmol/L (<50 mg/dL);

NewAmsterdam Pharma BV	CONFIDENTIAL	Statistical Analysis Plan
Protocol TA-8995-303		Version V2.0, 24 June 2021

- Pairwise comparisons among the various treatment groups for the change from Day 1 to Day 57, Day 1 to Week 12, and Day 1 to Week 16 in the mean trough plasma levels of obicetrapib; and
- Pairwise comparisons among the various treatment groups for the change from Day 1 to Day 57, Day 1 to Week 12, and Day 1 to Week 16 in CETP mass.

2.3.4 Safety Endpoints

The safety and tolerability profiles of obicetrapib alone, ezetimibe alone, and obicetrapib in combination with ezetimibe will be assessed by clinical laboratory values and the incidence of AEs.

3 STATISTICAL METHODOLOGY

3.1 General Considerations

3.1.1 Analysis Day

Analysis day will be calculated from the date of first dose of study drug. The day of the first dose of study drug will be Day 1 (Visit 2), and the day immediately before Day 1 will be Day -1. There will be no Day 0.

3.1.2 Analysis Visits

Scheduled visits will be assigned to analysis visits as recorded on the case report form (CRF). For participants who will be enrolled with Protocol Version 3.0 (02 September 2020), early termination visits will be assigned to analysis visits according to the following visit windows:

Analysis Visit	Target Analysis Day	Low Analysis Day	High Analysis Day
Day 1	1	NA	NA
Day 29	29	2	43
Day 57	57	44	71
Day 85	85	72	99
Safety Follow-up	113	100	126
PK Visit	141	127	

For participants who will be enrolled with Protocol Version 4.0 (14 January 2021), early termination visits will be assigned to analysis visits according to the following visit windows:

Analysis Visit	Target Analysis Day	Low Analysis Day	High Analysis Day
Day 1	1	NA	NA
Day 29	29	2	43
Day 57	57	44	71
Safety Follow-up	85	72	99
PK Visit	113	100	

Unscheduled visits recorded on the CRF will not be re-assigned and will remain labeled as unscheduled.

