#### 3.1.2 Treatment Period

Up to 2 weeks after the Screening Visit, participants will return to the site on Day 1 (Visit 2) to be randomized and begin treatment. Approximately 100 eligible participants (25 participants per treatment group) will be randomized in a 1:1:1:1 ratio to 1 of the following treatment groups:

- Combination therapy: 5 mg obicetrapib + 10 mg ezetimibe;
- Obicetrapib monotherapy: 5 mg obicetrapib + placebo ezetimibe;
- Ezetimibe monotherapy: placebo obicetrapib + 10 mg ezetimibe; or
- Placebo: placebo obicetrapib + placebo ezetimibe.

During the 8-week Treatment Period, the assigned study drugs will be administered by the participant orally and once daily on Days 1 through 57. Participants will return to the site every 4 weeks for efficacy, safety, PK, and CETP mass assessments. Participants, Investigators, the Clinical Research Organization, and the Sponsor will be blinded to all lipid results from Day 1 (Visit 2) for the first participant through the PK Visit (Visit 6) for the last participant in order to protect blinding to treatment assignment.

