# 5.5.3 Study Drug Administration

Study drugs will be administered by the participant orally and once daily on Days 1 through 57. Study drugs should be administered at approximately the same time each morning, with food. On days with visits scheduled, study drugs should be administered with food following all fasted blood samples. If a participant forgets to take study drug on a given day, they should take the next dose as normal and should not take a double dose to make up for the forgotten dose.

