#### 6.6 Early Termination Visit and Withdrawal Procedures

The end of the study for participants completing the study is Visit 6. For participants who are withdrawn from the study prior to completion, all of the following procedures will be performed at an Early Termination Visit:

- Record concomitant medications;
- Record weight;
- Perform physical examination;
- Obtain vital signs;
- Collect fasting (≥10 hours) blood samples for chemistry and hematology panels;
- Collect urine sample for urinalysis;

- Collect fasting (≥10 hours) blood sample for lipid profile;
- Perform study drug compliance check;
- Register visit in IRT; and
- Assess AEs.

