The primary efficacy analysis of the percent change from Day 1 to Day 57 in LDL-C will be performed using a mixed model for repeated measures (MMRM) approach. The analysis will include fixed effects for treatment, visit, and treatment-by-visit interaction, along with a covariate of the Baseline value as a continuous covariate. It is to note that randomization was stratified by categories of LDL-C value (<3.5 mmol/L [<135 mg/dL] or \ge 3.5 mmol/L [\ge 135 mg/dL]) only to ensure similar distribution of LDL-C across all treatment groups; however, the MMRM model will include the original scale of the LDL-C value as a continuous covariate. The Restricted Maximum Likelihood estimation approach will be used with an unstructured covariance matrix. The least squares means, standard errors, and 2-sided 95% confidence intervals for each treatment group, for the pairwise comparisons of the combination therapy, obicetrapib monotherapy, and ezetimibe monotherapy to placebo, and for the pairwise comparisons of combination therapy and obicetrapib monotherapy versus ezetimibe monotherapy will be provided. The treatment comparison will be performed using a 2-sided test at the $\alpha = 0.05$ level of significance.

The MMRM approach will include all available assessments of percent change in LDL-C from Baseline to Day 29, Day 57, and Day 85. The model assumes the data are missing at random (MAR). If any data are missing, the model will use all information from the other time points to estimate the mean treatment difference at the given time point. No imputation of missing data will be performed for the primary efficacy endpoint analysis.

The analysis will be implemented using SAS[®] Proc Mixed. The sample SAS code can be found below:

Note: USUBJID = unique subject identifier TREATMENT = 0 (Placebo), 1 (Ezetimibe monotherapy), 2 (Obicetrapib monotherapy), 3 (Combination therapy) VISIT = visit BASE = Baseline value PCHG = Percent change from Baseline proc mixed; class USUBJID TREATMENT VISIT; model PCHG = TREATMENT VISIT; model PCHG = TREATMENT BASE VISIT TREATMENT*VISIT / solution cl; Repeated VISIT / TYPE=UN sub=USUBJID; Ismeans VISIT*TREATMENT / cl diffs; run;

Sensitivity Analysis

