4.2 End of Double-Blind Treatment Analysis

An end of double-blind treatment analysis will be performed when all enrolled participants have completed the double-blind treatment and Safety Follow-up periods, or are withdrawn from the study. For participants enrolled under protocol amendment version 3.0 and earlier, the Safety Follow-up period will correspond to Visit 6 / Week 16. For participants enrolled under protocol amendment version 4.0, the Safety Follow-up period will correspond to Visit 5 / Week 12. The end of treatment analysis will be performed on all available efficacy and safety data as described in the above sections of the SAP.

After all enrolled participants have completed the double-blind treatment and Safety Follow-up periods and exclusions from analysis populations have been finalized, the randomized treatment assignments will be unblinded and the analysis will be generated. Following sponsor request to unblind after end of treatment, a subset of personnel at the Clinical Research Organization (Medpace, Inc.) who are not involved with the day-to-day operations of the study will be unblinded in order to generate the end of double-blind treatment analysis. In accordance with the protocol, the Sponsor will only receive end of treatment analysis containing unblinded information following the final participant completing the PK Visit (Visit 6). In addition to TFLs, SDTM data and ADaM data along with associated files will be provided. Associated files may include the following: annotated case report forms (CRFs), SDTM specifications, SDTM programs, ADaM specifications, ADaM programs, and TFL programs.

NewAmsterdam Pharma BV	CONFIDENTIAL	Statistical Analysis Plan
Protocol TA-8995-303		Version V2.0, 24 June 2021

The result of this analysis will be used to support regulatory submissions interactions.

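### For version 4.0 participants, the SAP's early-termination window labels lipid values taken up to about 14 days after the last scheduled dose as Day 57, with no rule for a second Day 57 record

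*SAP*

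**What the plan says.** - **Windows.** SAP 3.1.2 keeps scheduled visits under their CRF label and uses day windows only for early-termination visits. The version 4.0 table begins "For participants who will be enrolled with Protocol Version 4.0 (14 January 2021), early termination visits will be assigned to analysis visits". It gives Day 57 a low day of 44 and a high day of 71, and Safety Follow-up starts at Day 72. The Day 57 row is identical in the version 3.0 table, which has a further Day 85 visit before Safety Follow-up at Day 113.
- **Dosing.** Protocol 5.5.3: "Study drugs will be administered by the participant orally and once daily on Days 1 through 57".
- **What follows dosing.** SAP 4.2: "For participants enrolled under protocol amendment version 4.0, the Safety Follow-up period will correspond to Visit 5 / Week 12".
- **Who has an early-termination visit.** Protocol 6.6: "The end of the study for participants completing the study is Visit 6". Anyone withdrawn sooner has an Early Termination Visit, even after completing treatment. Its procedures include "Collect fasting (≥10 hours) blood sample for lipid profile".
- **What enters the primary model.** SAP 3.4.1: "The MMRM approach will include all available assessments of percent change in LDL-C from Baseline to Day 29, Day 57, and Day 85". The sample code has a REPEATED statement on visit within participant and an unstructured covariance.
- **What is removed.** The mITT definition (Protocol 9.1, SAP 3.2.2) drops only values obtained after a restricted lipid-altering therapy. The SAP sets no limit on time since last dose and does not say which of two values in one analysis visit is used.

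**The concern.** The primary endpoint is LDL-C at the end of the 8-week Treatment Period. Under the version 4.0 schedule, the second half of the Day 57 window lies after the last scheduled dose. LDL-C on active drug would be expected to move back toward baseline during that time, while on placebo it has no drug effect to lose.

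The unchanged limit looks like an incomplete update. The version 3.0 table has a Day 85 visit ahead of Safety Follow-up, and SAP 3.3.7 still has exposure categories up to 12 weeks. Together these suggest that dosing under version 3.0 ran to about Day 85, which would have made Days 58 to 71 on-treatment days. That is an inference; the documents do not state it.

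Two things are at stake: a modest bias in the Day 57 estimates, and an unwritten choice left to the programmer in the primary analysis. The same label could also let a participant who missed Visit 4 meet the Per-Protocol requirement for a Day 57 LDL-C value, unless a major deviation excludes them. It could also supply the Day 57 value for the LDL-C target proportions.

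**Working it through.** **1. The plan's own figure.** Inputs from SAP 2.2.4: 25 per group, difference 30 points, SD 15, two-sided alpha 0.05. Standard error of the difference = 15 × √(2/25) = 4.24. Power ≈ Φ(30/4.24 − 1.96) = Φ(5.11), above 99.9%. The stated power of more than 90% is reproduced; 6 per group would already give 90%.

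**2. Days after dosing.** The window has 71 − 44 + 1 = 28 days. Days after Day 57: 71 − 57 = 14. Visit 4 may fall as late as Day 60, and Protocol 6.3.3 has study drug taken after that visit's samples, so Days 58 to 60 are not clearly off drug. Days 61 to 71 are 11 days.

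**3. Two routes.**
- *Visit 4 missed, early termination on Day 70.* The value is taken 70 − 57 = 13 days after the last scheduled dose and is the only Day 57 value.
- *Visit 4 on Day 57, withdrawal on Day 66.* The Visit 4 value keeps its CRF label. The Day 66 value, 9 days after the last scheduled dose, is also labelled Day 57. The code needs one record per participant and visit, so someone must choose a value before the model can be fitted.

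**4. Size against placebo, first route.** Let k be the number of active-arm participants, of 25, whose sole Day 57 value is a washout value, and w the fraction of the effect lost by then. The documents give neither, so both are assumed. On simple arm means, shift in the difference = 30 × w × k/25 points:

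| k | w = 0.25 | w = 0.5 | w = 1 |
|---|---|---|---|
| 1 | 0.3 | 0.6 | 1.2 |
| 2 | 0.6 | 1.2 | 2.4 |
| 3 | 0.9 | 1.8 | 3.6 |
| 5 | 1.5 | 3.0 | 6.0 |

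**5. Primary power, worst cell (k = 5, w = 1).** Difference = 30 × (1 − 5/25) = 24. The mixture adds variance (5/25)(20/25)(30²) = 144 in the active arm. Standard error = √((225 + 144)/25 + 225/25) = 4.87. Power ≈ Φ(24/4.87 − 1.96), about 99.8%.

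**6. Ezetimibe versus placebo.** Protocol 1.4 cites an 18.58% reduction against placebo. With SD 15, power is 99.2% undiluted, 96.0% at k = 3 and w = 1, and 91.1% at k = 5 and w = 1.

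**7. Contrasts against ezetimibe.** Three of the seven secondary endpoints compare an active arm with ezetimibe. For LDL-C, one washout value in the ezetimibe arm weakens that arm by 18.58 × w/25 = 0.19 to 0.74 points (w = 0.25 to 1), which enlarges the difference. A washout value in the other arm narrows it. Values in both arms partly cancel.

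**The case against.** The case for leaving the window alone has several parts.

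- **It is an ordinary midpoint window.** Days 44 to 71 fit visits at Days 29, 57 and 85, and the mITT rule removes values only after other lipid therapy, so keeping off-drug values breaks no written rule. This is correct. It does not settle which record to use, and the SAP does not say that off-drug values are meant to count as end-of-treatment values.
- **The route is narrow.** It needs a withdrawal visit on Days 58 to 71, when only a late Visit 4 is otherwise scheduled. No dropout or washout rate is given, and one value shifts the primary difference by at most 1.2 points against a standard error of 4.24. This stands, and it limits the point to estimation and pre-specification.
- **A selection rule may exist elsewhere.** SAP section 6 defers detailed programming specifications to a separate document. That cannot be excluded, but a rule affecting the primary endpoint belongs in the SAP text.
- **A partial check exists.** LDL-C by ultracentrifugation is scheduled only at Visits 2 and 4, so the third sensitivity analysis, as scheduled, has no early-termination values. This helps in reading the primary result but does not repair it.

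Three stronger readings are tempting, and the documents do not support them. A reader might infer that an early-termination value replaces a true Visit 4 value; scheduled visits keep their CRF label, and no text permits overwriting. A reader might infer that every lipid contrast is diluted alike; those against ezetimibe need not be. A reader might infer that all of Days 58 to 71 are off drug; the Visit 4 window makes Days 58 to 60 uncertain.

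**Conclusion.** The point holds as a gap in the SAP. Followed as written for version 4.0 participants, section 3.1.2 either models a post-dosing lipid value as Day 57 or produces two Day 57 records that the sample code cannot take, with no stated way to choose.

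Against placebo the bias is dilution. It is 0.3 to 1.2 points per sole value in an arm of 25, assuming that 25% to 100% of the planned 30-point difference is lost by the draw. The number of such values is unknown. Against ezetimibe the direction depends on the arm affected.

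The primary conclusion is not threatened, since power stays at about 99.8% even with five complete-washout values. Confidence is high that the rule is missing. The size of the effect rests on assumptions alone.

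**What to change.** Amend SAP 3.1.2 before database lock and unblinding, for efficacy lipid endpoints only:

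1. For version 4.0 participants, end the Day 57 early-termination window at Day 60, which is the protocol's own +3-day limit for Visit 4.
2. List later early-termination lipid values, but do not model them as Day 57.
3. State that a scheduled Visit 3 or Visit 4 value takes precedence over an early-termination value in the same window.

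Leave the windows for safety data unchanged. Moving them for all data would relabel early-termination laboratory values and vital signs taken soon after the last dose as Safety Follow-up.

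The cost is one changed limit, restricted to lipids, and two short statements. Sample size, visits and dosing are unaffected. A scheduled Visit 4 that runs late keeps its CRF label. The small downside is that a participant who missed Visit 4 and terminated on Days 61 to 71 has a missing Day 57 value, which the mixed model already handles under missing at random.

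The change does not deal with off-drug values before Day 57 in participants who stop early. Those would need a time-since-last-dose rule or an explicit statement that such values are kept.
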